9 STUDY OBJECTIVES

9.1 Primary Study Objective

The primary objective is to evaluate the safety and tolerability of three doses of two dose levels of ZH9PA and of three doses of a single dose level of a combination of ZH9 and ZH9PA over 12 weeks (up to Day 84) after the first dose of vaccine.

9.2 Secondary Study Objective

- To evaluate serum IgA and IgG responses against the following antigens: - *S. enterica* Ser. Paratyphi A LPS 0:2 and Flagella H:a and *S. enterica* ser. Typhi LPS O:9 and Flagella H:d, induced by three vaccine doses, of two dose levels (1×10^9 CFU and 1×10^{10} CFU) of ZH9PA alone or in combination with 1×10^{10} CFU ZH9, up to Day 84 after the first dose of vaccine (Day 0).
- To evaluate the mucosal IgA immune responses to LPS 0:2, LPS O:9, Flagella H:a and Flagella H:d, at 7 days after each vaccination, as determined by ALS assay.
- To evaluate Serum IgA and IgG responses against the four antigens, induced by each of the first two vaccine doses, on Days 21, and 42, by blood samples taken prior to each participant receiving the next dose of vaccine or placebo.
- To evaluate the safety profile of the ZH9PA and combination ZH9/ZH9PA vaccines, over the 6 months following the third dose of vaccine.

10 INVESTIGATIONAL PLAN

10.1 Overall Study Design and Plan

This is a Phase I, randomised, double-blind, placebo-controlled, parallel group, single-centre study involving 45 healthy participants. The aim is to evaluate a combination vaccine against enteric fever comprising the live attenuated *Salmonella* strain ZH9 (previously tested in a number of clinical trials as a typhoid vaccine) and its modified derivative, ZH9PA, in which the typhoid antigens LPS O:9 and Flagellin H:d have been substituted by the Paratyphi A antigens, LPS O:2 and Flagellin H:a. ZH9PA has not previously been tested in humans; therefore, the first two cohorts comprise a dose escalation of this component alone, followed by a final cohort in which the combination is tested at a single dose level.

There will be 3 cohorts:

Cohort 1 will consist of 9 participants, who will receive 3 doses of 1×10^9 CFU of ZH9PA (6 participants) or placebo (3 participants).

Cohort 2 will consist of 18 participants, who will receive 3 doses of 1×10^{10} CFU of ZH9PA (12 participants) or placebo (6 participants).

Cohort 2 will not be initiated until all 9 participants of Cohort 1 have received 1 dose of ZH9PA or placebo, and the safety data, up to Day 7 are available. These safety data will be assessed by the safety review group, at which point the decision will be made as to whether proceeding with administration of the first dose of the higher dose level of ZH9PA (1×10^{10} CFU) to Cohort 2 is appropriate.

Cohort 3 will consist of 18 participants, who will receive 3 doses of 1×10^{10} CFU of ZH9PA and 1×10^{10} CFU of ZH9 (12 participants) or placebo (6 participants).

Cohort 3 will not be initiated until a minimum of 14 participants of Cohort 2 have received 1 dose of ZH9PA or placebo, and the safety data, up to Day 7 are available. These safety data will be assessed by the safety review group, at which point the decision will be made as to whether proceeding with administration of the first dose of the combination of ZH9PA and ZH9 to Cohort 3 is appropriate. In the event that fewer than 18 participants are dosed in Cohort 2, the remaining participants to complete the required number will be dosed with Cohort 3 or as a straggler group.

Each cohort will start with a sentinel group that will consist of 2 participants, 1 will receive placebo and 1 will receive the relevant vaccine for that cohort. No further participants will be dosed until 24 hours after the second participant has received his/her dose. The rest of the cohort will be dosed provided there are no safety issues identified by the Investigator. This design allows maintenance of the “blind” until Day 70.

The clinical phase is anticipated to take place in Q4 2019 and Q2 2020. The end of the study is defined as last participant last visit.

The study will take place in the Clinical Pharmacology Unit of Simbec-Orion (Clinical Unit) under full medical and nursing supervision.

A schedule of all study assessments is provided in [Table 10.7.1](#).

Screening (Day -28 to Day -1)

Screening assessments will be performed from Day -28 to Day -1 to ensure the eligibility of participants. Assessments will be performed as per [Table 10.7.1](#).

Treatment Period (Day 0 to Day 84)

Participants will be admitted to the Clinical Unit on the morning of Day 0 with confirmation of eligibility and baseline assessments performed as per [Table 10.7.1](#). Following a 90 minute (min) fast prior to dose administration, participants will receive the first dose on Day 0, and then continue to fast for a further 90 mins post dose administration; water will be allowed. Following the completion of the 4h post-dose assessments and at the discretion of the Investigator, the participants will be discharged from the Clinical Unit. Participants will return to the Clinical Unit on Day 3 for safety assessments as per [Table 10.7.1](#). For the 7 days following the first dosing visit (Day 1 to Day 7) participants will be required to record their body temperature at home twice a day i.e. once in the morning and once in the evening (a thermometer and a diary will be provided to record body temperature). Participants will return to the Clinical Unit on Day 7 with the diary and to give a blood sample for the peripheral blood mononuclear cells (PBMC)/ALS assay; assessments will be performed as per [Table 10.7.1](#). Participants will return to the Clinical Unit on Day 14 for safety assessments; assessments will be performed as per [Table 10.7.1](#).

Participants will be admitted to the Clinical Unit on the morning of Day 21, with assessments performed as per [Table 10.7.1](#). Following a 90-min fast prior to dose administration, participants will receive the second dose, and then continue to fast for a further 90 mins post dose administration; water will be allowed. Following the completion of the 4h post-dose assessments and at the discretion of the Investigator, the participants will be discharged from the Clinical Unit. Participants will return to the Clinical Unit on Day 24 for safety assessments as per [Table 10.7.1](#). For the 7 days following the second dosing visit (Day 22 to Day 28) participants will be required to record their body temperature at home twice a day, i.e. once in the morning and once in the evening (a thermometer and a diary will be provided to record body temperature). Participants will return to the Clinical Unit on Day 28 with the diary and to give a blood sample for the PBMC/ALS assay; assessments will be performed as per [Table 10.7.1](#).

Participants will be admitted to the Clinical Unit on the morning of Day 42, with assessments performed as per [Table 10.7.1](#). Following a 90-min fast prior to dose administration participants will receive the third dose, and then continue to fast for a further 90 mins post dose administration; water will be allowed. Participants will return on Day 45 for safety assessments as per [Table 10.7.1](#). For the 7 days following the third dosing visit (Day 43 to Day 49) participants will be required to record their body temperature at home twice a day, i.e. once in the morning and once in the evening (a thermometer and a diary will be provided to record body temperature). Participants will return to the Clinical Unit on Day 49 with the diary and to give a blood sample for the PBMC/ALS assay; assessments will be performed as per [Table 10.7.1](#).

Participants will return to the Clinical Unit on Day 70 to provide a stool sample for bacteriology. If the stool sample is positive for any *Salmonella* strain at Day 70, it will be presumed to be one of the vaccine strains, and participants will be asked to return to the Clinical Unit to receive a course of antibiotic therapy. Participants who receive a course of antibiotics will be required to provide a repeat stool sample for bacteriology testing on Day 84, to confirm that shedding of the vaccine strains has ceased, as per [Table 10.7.1](#).

Post-Study Follow-Up (Day 85 to Day 224)

Safety follow-up telephone calls will be performed on Days 154 and 224 following the first dose of study vaccine administration to check the general health of the participant and to review clinically relevant AEs. Clinically relevant adverse events are adverse events that required a visit to a healthcare professional. Assessments will be performed as per [Table 10.7.1](#).

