10.6.4.2 Treatment Period

The following IMPs will be administered:

Cohort 1 (n=9)	3 doses of 1×10^9 CFU of ZH9PA (6 participants) Placebo (3 participants)
Safety Review Meeting (up to Day 7 safety data)	
Cohort 2 (n=18)	3 doses of 1×10^{10} CFU of ZH9PA (12 participants) Placebo (6 participants)
Safety Review Meeting (up to Day 7 safety data)	
Cohort 3 (n=18)	3 doses of 1×10^{10} CFU of ZH9PA and 1×10^{10} CFU of ZH9 (12 participants) Placebo (6 participants)

The IMPs will be administered following 90 mins of fasting (water is permitted).

A dose leader design will be implemented with 2 participants being dosed on the first dosing day of EACH cohort. Of these 2 participants, 1 will be randomised to receive active drug and 1 randomised to receive placebo. The remainder of the cohort will be randomised and dosed at least 24 h later pending an acceptable safety profile in the dose-leader group and will contain at least 1 additional placebo participant. The decision to proceed will be confirmed by the Investigator or delegate and communicated with the Sponsor. This design allows maintenance of the “blind”.

IMP administration will be documented in the eCRF.

There will be 21 days between doses.

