10.6.8 Timing of Dose for Each Participant

Two (2) dose leaders (1 active:1 placebo) will be dosed first in each cohort. The remainder of the cohort will be dosed at least 24 h later pending an acceptable safety profile in the dose-leader group. A telephone call will be made to the dose leaders on the morning of Day 1 to assess the safety profile.

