Concomitant Medication	X	X	X	X	X	X	X	X	X	X	X	X	X	X	X

Study Flow Chart Footnotes:

All procedures on dosing days (Days 0, 21, 42) are to be completed prior to dosing (except post dosing vital signs and health check for discharge)

¹ The treatment period will be approximately 85 days duration, from the first dosing day (Day 0) until Day 84 (inclusive).

² Post-study follow-up telephone call will be performed on Days 154 and 224 after receiving the first dose of IMP (Day 0).

³ Eligibility will be confirmed prior to dose administration on Day 0, Day 21 and Day 42.

⁴ For female participants only.

⁵ For postmenopausal female participants only

⁶ At Day 0, Day 21, and Day 42, vital signs to be performed pre-dose and at 4 hours post-dose.

⁷ IMP will be administered fasted (90 mins prior to dose administration). Participants will fast for a further 90 mins post each dose administration. Participants in sentinel cohorts will be contacted by telephone approximately 24 hours following the Day 0 dose to assess their safety profile.

⁸ Participants to record body temperature twice daily at home for 7 days post administration of each dose of IMP.

⁹ Blood cultures to be performed to identify vaccine strains only if a participant experiences defined symptoms (e.g., fever greater than 37.8°C, white blood cell (WBC) >20x10⁹ cells/L, respiratory rate >25 breaths per min, pulse rate >130 beats per min (bpm)) or clinically indicated.

¹⁰ Participants will attend the Clinical Unit on Day 70 to provide a stool sample. If the stool sample is positive for any *Salmonella* strain at Day 70, it will be presumed to be one of the vaccine strains, and participants will be asked to return to the Clinical Unit to receive a course of antibiotic therapy, and a repeat stool culture will be obtained on Day 84 to confirm shedding of *Salmonella*, presumed to be one of the vaccine strains, has ceased.

¹¹ Samples to be collected prior to each dosing.

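### No temperature is scheduled for the dose leaders between 4 h after dosing and the Day 1 morning, so a 12 h fever on the first evening can leave no raised scheduled reading at cohort release or at the Day 7 review

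*Combined protocol and SAP*

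**What the plan says.** All references are to the protocol.

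- **Clinic readings.** Oral temperature is one of the vital signs (section 10.7.1.3.3). On dosing days the flow chart footnotes have "vital signs to be performed pre-dose and at 4 hours post-dose" (Table 10.7.1, footnote 6).
- **Discharge.** "Following the completion of the 4h post-dose assessments and at the discretion of the Investigator, the participants will be discharged from the Clinical Unit" (section 10.1).
- **Home diary.** "For the 7 days following the first dosing visit (Day 1 to Day 7) participants will be required to record their body temperature", once each morning and once each evening (section 10.1). The same pattern follows doses 2 and 3, on Days 22 to 28 and Days 43 to 49. Footnote 8 of Table 10.7.1 speaks only of 7 days after each dose and gives no starting time. The diary comes back a week later: "Participants will return to the Clinical Unit on Day 7 with the diary".
- **Contact during the hold.** "A telephone call will be made to the dose leaders on the morning of Day 1 to assess the safety profile" (section 10.6.8). Footnote 7 of Table 10.7.1 times it slightly differently: "Participants in sentinel cohorts will be contacted by telephone approximately 24 hours following the Day 0 dose to assess their safety profile". Neither place mentions temperature. The call is kept in a log book (Table 10.8.1).
- **Release.** The hold lasts 24 h from the second leader's dose. "The rest of the cohort will be dosed provided there are no safety issues identified by the Investigator" (section 10.1). "The decision to proceed will be confirmed by the Investigator or delegate and communicated with the Sponsor" (section 10.6.4.2).
- **Escalation.** The review before the next cohort uses safety data up to 7 days after the first dose, including participants' own temperature records (section 10.2.1). A related fever above 38.5°C for 12 h or more in one sentinel participant pauses escalation (section 10.2.2.2).

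**The concern.** The hold exists so that an early reaction in the first person given vaccine at each step is seen before others are exposed. ZH9PA has not been given to humans before. Each cohort has one vaccinated dose leader, and release opens dosing to 5, 11 and 11 further vaccine recipients in Cohorts 1, 2 and 3 (6 − 1, 12 − 1 and 12 − 1).

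The protocol relies on measured temperatures from Day 1 onward, but not on the first evening and night. That stretch is longer than the 12 h which the protocol itself uses to define a persistent fever. A fever that begins after the 4 h reading and ends before the next morning's reading would leave no scheduled reading above normal. It would be known at release only if the participant noticed it and said so. The diary holds no Day 0 evening entry, so the self-recorded temperatures would not show it at the Day 7 review either, and that is where the fever criterion formally applies.

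**Working it through.** The protocol gives no figure for this interval, so there is none to reproduce.

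**Inputs from the protocol:** a reading 4 h after dosing; the next reading on the Day 1 morning; a 24 h hold; a fever criterion of 12 h.

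**Assumptions:** dosing at 08:00 to 12:00 (the protocol says only that admission is in the morning); Day 1 reading at 07:00 to 09:00; a sustained fever of length D; and, for the shares only, onset equally likely at any time in the gap.

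**Step 1: length of the gap.** G = (24 + Day 1 reading time) − (dose time + 4).

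| Dose | 4 h reading | G, Day 1 reading at 07:00 | at 08:00 | at 09:00 |
|---|---|---|---|---|
| 08:00 | 12:00 | 19 h | 20 h | 21 h |
| 09:00 | 13:00 | 18 h | 19 h | 20 h |
| 10:00 | 14:00 | 17 h | 18 h | 19 h |
| 11:00 | 15:00 | 16 h | 17 h | 18 h |
| 12:00 | 16:00 | 15 h | 16 h | 17 h |

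Within a leader's own 24 h hold the gap cannot exceed 24 − 4 = 20 h. In the 08:00/09:00 cell the reading comes 25 h after dosing, so only 20 of its 21 h count towards that leader's hold. The range is therefore 15 to 20 h: 15/24 = 63% and 20/24 = 83%. An earlier Day 1 reading does not remove the problem: a 12:00 dose and a 06:00 reading give G = 30 − 16 = 14 h, still above 12 h.

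**Step 2: onset times that leave no raised scheduled reading.** The fever must start after dose + 4 h and end before the Day 1 reading, which is a window of G − D hours. For D = 12 and G from 15 to 20 h the window is 3 to 8 h wide. It opens at 12:00 to 16:00 and closes at 19:00 to 21:00.

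As a share of fevers starting in the gap, max(0, G − D)/G:

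| Fever length | G = 15 h | G = 18 h | G = 20 h |
|---|---|---|---|
| 12 h | 3/15 = 20% | 6/18 = 33% | 8/20 = 40% |
| 15 h | 0/15 = 0% | 3/18 = 17% | 5/20 = 25% |

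These shares apply only if such a fever occurs.

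**Step 3: timing of the call.** If the call comes 24 h after dosing, it falls at the dosing clock time on Day 1. In 14 of the 15 cells above that is at or after the morning reading; the exception is 08:00/09:00.

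**Step 4: effect of an evening reading.** It splits G into g1 (from the 4 h reading to the evening) and g2 (from the evening to the Day 1 morning). A fever is missed only if g1 or g2 exceeds D.

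- At 21:00: g1 is 5 to 9 h and g2 is 10 to 12 h, so no 12 h fever falls wholly between readings.
- At 22:00: g1 is 6 to 10 h and g2 is 9 to 11 h, with the same result.
- At 20:00: g1 is 4 to 8 h. g2 is 11 to 12 h if the morning reading is by 08:00, which is enough. With a 09:00 reading g2 is 13 h, leaving a window of 1 h.
- At 18:00: g2 is 13 to 15 h, leaving a window of 1 to 3 h, so this is too early.

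**The case against.** The strongest reply is that several things must coincide before anyone is harmed. A persistent fever must start within a few hours of the 4 h reading, resolve before the morning, and go unmentioned at a call made specifically to assess safety. The participant would probably be awake at onset and may well report it. Discharge is at the Investigator's discretion, and release needs an acceptable safety profile and communication with the Sponsor. All adverse events are recorded with onset and resolution times, and later cohorts wait for a Day 7 review. All of this stands, and it limits the weight of the point. It does not put a reading into the gap.

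A reader might infer more than the documents support:

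- *That the fever criterion in section 10.2.2.2 governs sentinel release.* It is a dose-escalation rule. Release rests on the Investigator's judgement.
- *That 21 h, or 88% of the hold, goes unmeasured.* The most that fits in a leader's own 24 h is 20 h, or 83%.
- *That the call comes before the morning reading.* At about 24 h after dosing it normally comes at or after it (step 3). What the protocol does not say is that the reading is asked for.
- *That the first night is the key window for systemic infection.* Section 10.3 ties the diary to that risk, but section 8 places bacteraemia after 8 to 14 days of multiplication in natural disease. The point here is early reactogenic fever.

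Some documents are not available. The call log and the diary card may ask for more than the protocol does. The temperature row of Table 10.7.1 shows no marks in the text available, so it cannot settle the start of the diary. The explicit days in section 10.1 are the better guide. If a Day 0 evening reading is intended under footnote 8, section 10.1 needs to say so.

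**Conclusion.** The point holds as a minor safety improvement. On the protocol text, the dose leaders have no scheduled temperature between 4 h after dosing and the Day 1 morning. The gap exceeds 12 h at every clock time tried. A fever of the length named in the escalation criterion can therefore leave no raised scheduled reading at release or in the Day 7 diary data.

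The 15 to 20 h range rests on assumed clock times, and the shares of 20 to 40% for a 12 h fever also assume uniform onset. They describe the schedule and are not a participant's risk. The documents give no absolute fever risk, and only three dose leaders in the trial receive vaccine. It would be wrong to conclude that a sentinel fever would go unknown, or that the escalation rule cannot work: a reported fever still reaches the Investigator and the adverse event record.

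**What to change.** 1. In section 10.1 and footnote 8 of Table 10.7.1, start the home diary on the evening of dosing, at minimum on Day 0 for the two dose leaders of each cohort. Keep the evening and Day 1 morning readings no more than 12 h apart, for example with an evening reading at about 21:00 to 22:00.
2. In section 10.6.8 and footnote 7, have the Day 1 call record the temperatures since discharge, including the morning reading, and any paracetamol taken. Paracetamol is permitted and already goes into the eCRF (section 10.6.10). Asking at the call makes it known before release.

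**Cost.** Protocol and diary wording, two questions at a call already planned, and 2 × 3 = 6 extra self-readings in the minimum version. Extending it to every participant and every dose means 45 × 3 = 135 readings. A thermometer is already provided for the home diary.

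**Limits.** The added reading gives the Investigator a raised value to act on. It does not by itself prove 12 h of fever, because two raised readings less than 12 h apart cannot show that duration. An isolated raised evening value may also need the Investigator's judgement before release.
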